Trial stopping rules were approved by the Data Safety and Monitoring Board for the following events:

a. Undue inducement

To detect if incentives represent undue inducement that could distort voluntary informed consent, the research team will test the statistical interaction between incentive size and risk perception on the outcome of enrollment in the parent RCT.

b. Unjust inducement

To assess the presence of unjust inducement, or preferential participation among participants with either (a) lower income, or (b) reduced financial well-being, two interaction terms will be evaluated in separate models to avoid collinearity. Unjust inducement will be defined as a statistically significant interaction between (a) incentive size and annual household income, or (b) between incentive size and economic well-being, each on the outcome of trial enrollment. One or both of these interactions, if statistically significant in the direction that lower-income persons or persons with reduced economic well-being are more strongly motivated to participate by increasingly large payments, will be considered grounds for terminating the trial or suspending a trial arm.

10. Timing of analysis and adjustment of significance level

Interim analyses will be conducted after 50% and 75% of the data have accrued within each the BASC and MOVE IT trials. In contrast to the final analyses, which will be structured as tests of non-inferiority, the interim analyses will be conducted as superiority tests of the interactions, such that rejection of the null hypothesis indicates evidence of the presence of an interaction between incentive size and one of our three primary covariates. We will use 1-sided significance levels of 0.0055, and 0.0219.

11. Personnel

Interim analyses will be performed by the trial's primary statistician who will conduct all analyses blinded to trial arm. Investigators, the project manager, and the DSMB will remain blinded to treatment arm through completion of analyses. The data manager and faculty statistician have been unblinded as was necessary to perform essential functions of their roles.

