Participants will be randomized to the 3 experimental arms (low-, middle-, and high-level incentive) in equal, 33.3% probabilities. A Penn analyst will implement block randomization stratified by site in the BASC parent trial and stratified by clinical research coordinator in the MOVE IT trial. The trial's primary statistician on the Penn research staff will provide a block randomization scheme for each clinical research coordinator (MOVE IT) and will upload a CSV file to the REDCap randomization module. He/she will also provide a block randomization scheme for each site for the Access Data Management System (BASC) (see Section 10.a.1. Data Management – BASC). The parent trial research staff will respond to initial eligibility prompts n the REDCap software through an initialization step and will immediately receive the randomization assignment for that participant. Randomization will take place in the DMS for the BASC trial. This will allow them to message to the participant the appropriate incentive level for participation in the parent trial, and present the correct paper consent based on their arm assignment (see Sections 8.g. Parent Trial Informed Consent).

i. BASC

Randomization and group assignment occurs after pre-screening data are collected and RETAIN eligibility probes are administered on the eligibility pre-screening call for the BASC parent trial (see Section 8.e.2 Administration of Survey Instruments – BASC). Research staff will know group assignment when patients are first introduced to the BASC trial on the phone in order to message the assigned payment (\$0, \$200, \$500) for the participant. Participants who are deemed preliminarily eligible will schedule an intake session, where they will view the electronic BASC parent trial consent form (\$0, \$200, or \$500) and receive a paper copy of the form with respective incentive information.

ii. MOVE IT

Randomization and group assignment occur after MOVE IT screening steps (see Section 8.e.3 Administration of Survey Instruments – MOVE IT) following clinical research coordinators' brief introduction to the study upon entering patients' hospital room. Clinical research coordinators will randomize patients and know the group assignment as they complete the recruitment script and assess patients' interest in learning about the MOVE IT trial. Assignment occurs prior to registering the patient in the Way to Health platform used for survey administration.

8. Study Procedures

a. Screening

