In the BASC study, final determination of parent trial eligibility may not take place until labs are conducted at the baseline intake session, following participants' signature of the parent trial consent form. However, initial eligibility screening on the pre- screen eligibility call will enable the BASC research team to determine which participants may be assessed for RETAIN eligibility.

In the MOVE IT study, clinical research coordinators will pre- screen participants for parent trial eligibility prior to the initial approach on the inpatient wards. However, final eligibility determination will take place immediately after coordinators' initial approach once smartphone ownership and patients' participation status in other physical activity trials is ascertained.

a. Eligibility

Using methods employed by PI [name] in several prior studies,^{29,30,64} parent trial research staff will use prompts to assess participants' prior knowledge about the RETAIN study in the BASC study. Prompts will not be used in the MOVE IT study, as we do not anticipate contamination among patients on the general medicine and oncology wards of the hospital; no two patients will be approached in the same room at once; and readmitted patients will not be re-approached.

b. Inclusion of Women and Minorities

No participants will be excluded from study participation based on gender, race, or ethnicity. We expect that enrollment of participants from The University of Pennsylvania Perelman Center for Advanced Medicine, Northwestern University out-patient clinics and the Hospital of the University of Pennsylvania inpatient clinics will result in study populations that closely reflect the underlying outpatient populations at these facilities in terms of gender, race, and ethnicity. These populations are also reflective of the broader populations of the Philadelphia, Chicago, Houston, St. Louis, and Boston metropolitan areas.

c. Informed Consent for RETAIN in BASC and MOVE IT

The sole informed consent processes used in both BASC and MOVE IT will be for the parent trials (see Section 8.f Parent Trial Informed Consent). Randomization and enrollment to RETAIN in the BASC and
MOVE IT studies will be carried out under a Waiver of Informed Consent, approved by the University of Pennsylvania Review Board. BASC participants deemed eligible for BASC via phone pre-screening and RETAIN. MOVE IT participants will be randomized immediately after eligibility screening in their hospital rooms.

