	secondary	risk score distributions. We found that in the Ambulation trial the
	analysis of the	risk score mostly (>85%) clumped on 0, and in the smoking trial the
	risk score and	score is extremely right skewed. To better handle this sparsity of
	incentives where	data we planned a secondary analysis in which we treat the risk
	risk score is	scores as binary and compare the inferences.
	treated as a	
	binary variable (0	
	and >0).	

VI. Final Statiscal Analysis Plan

1. Background and rationale

This study is designed to provide the first-ever real-world tests of a broad range of intended and unintended consequences of financial incentives for research participation. It will do so through the conduct of two separate, but similarly designed, embedded randomized trials within actual parent clinical trials. It is our hope the findings from this study will inform research regulations and guide the use of incentives in future RCTs so as to expedite medical innovation and improve health

2. Objectives and hypotheses

The aims of this study are to (1) determine if the ethical concerns with incentives for research participation actually manifest; and (2) assess the possible scientific and ethical benefits of financial incentives for RCT participation.

We hypothesize that research incentives will:

- Augment participants' perceptions of risk without disproportionately encouraging economically disadvantaged participants to enroll
- Demonstrate an increased enrollment fraction in the parent trials, thereby enhancing the scientific value and validity of the research by augmenting the precision of the studies

3. Design and randomization

RETAIN comprises two prospective randomized controlled trials, embedded within two parent trials conducted in parallel, each comparing three intervention arms. Arms vary by the amount of the financial incentives that are offered to potential participants. Amounts offered differ on a per trial basis determined by the relative time and effort being asked of the participant for each parent trial. Assignment to arms is determined by computerized random-number generation with block randomization using variable block sizes of 3 and 6. Participants in both embedded trials have a 33.3% probability of being assigned to each RETAIN arm.

a. BASC Trial

• The Behavioral Activation and Varenicline for Smoking Cessation in Depressed Smokers Study (BASC) (NCT 02378714)

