- Tests two behavioral interventions in combination with Varenicline in a population of daily smokers with current or lifetime major depressive disorder
- Eligible patients are randomized to receive inform consent forms offering \$0, \$200, or \$500 incentives for participation
- Patients are enrolled at The University of Pennsylvania and Northwestern University; randomization is stratified by site

b. MOVE IT Trial

- The Mobility and Outcomes for Validated Evidence Incentive Trial (MOVE IT) (NCT 03321279)
- Aims to examine the impact of a supportive social incentive-based gamification intervention in the three months post-hospital discharge among general medical and cancer patients using wearable technology
- Eligible patients are randomized to receive inform consent forms offering \$0, \$100, or \$300 incentives for participation
- Patients are enrolled at the Hospital of the University of Philadelphia by a team of clinical research coordinators; randomization is stratified by clinical research coordinator
- By necessity, clinical research coordinators administering the consent process in both parent trials are unmasked to the incentive information being messaged to prospective participants. The introduction to the study and the informed consent process have been robustly scripted for research staff involved in both trials to ensure that messaging is consistent and biases are minimized.

4. Population

Eligibility for RETAIN is contingent on eligibility for the BASC and MOVE IT parent trials.

- Adults age 18 years or older who are daily smokers with current or lifetime major depressive disorder without psychotic features (BASC)
- Adults age 18 years or older who are admitted for inpatient care to the Hospital of the University of Pennsylvania (HUP) on medicine or oncology floors (MOVE IT)

Patients randomized to RETAIN must be:

- Eligible for parent RCT
- 18 years or older
- English-speaking

In the BASC trial, prior knowledge of the incentive randomization or payment equalization used for this

study, which will be assessed with open-ended prompts during the first encounter, is an exclusion criterion. We will not assess for prior knowledge in the inpatient MOVE IT study population. However, only one patient per hospital room will be approached for the MOVE IT study to protect against contamination.

5. Primary outcome and analytic method

a. Primary outcome

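### In MOVE IT the next incentive offer is substantially predictable to the coordinator who recruits and randomises (about 58% correct guesses against 33% by chance), so allocation concealment is weakened.

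*Combined protocol and SAP*

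**What the plan says.** Final SAP, section 3 (Design and randomization), sets "block randomization using variable block sizes of 3 and 6" for both embedded trials and states that "Participants in both embedded trials have a 33.3% probability of being assigned to each RETAIN arm". The proportion of blocks of each size is not given. For MOVE IT the same section says that "randomization is stratified by clinical research coordinator".

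Final protocol, section 7.b (Assignment), says that the statistician "will provide a block randomization scheme for each clinical research coordinator (MOVE IT) and will upload a CSV file to the REDCap randomization module". Section 7.b.ii adds: "Clinical research coordinators will randomize patients and know the group assignment as they complete the recruitment script".

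Under section 8.a (Screening), "final eligibility determination will take place immediately after coordinators' initial approach". The survey-administration part of section 8, under MOVE IT, has coordinators find patients through the health record, ask two screening questions, randomise in real time and then state the amount. SAP section 3 accepts that "clinical research coordinators administering the consent process in both parent trials are unmasked to the incentive information being messaged to prospective participants", and offers scripting of the introduction and consent process as the safeguard.

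Neither document says that block sizes are withheld from coordinators, sets an order of approach, or discusses predictability. The centre fixed effect in SAP section 5.c applies to parent trials with several centres. No coordinator term is named for MOVE IT, and coordinator is not in Table 1.

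**The concern.** Once the amount is read out, unmasking cannot be avoided. Foreknowledge before assignment can be. Here it arises because the randomisation stratum is the recruiter: each coordinator sees every past assignment on a short-block list that only they use. With three arms, once two different offers have been made at the start of a block, the third becomes the most likely next one.

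The primary outcome is consent, obtained by the person who can anticipate the offer. If the coordinator's expectation affects, even unintentionally, which patient on the screening list is approached next, the arms can differ in willingness to enrol before any offer is made. That would distort the enrolment contrast, and it could distort the income and economic well-being interactions if the choice followed apparent financial need. Intention-to-treat analysis protects only after randomisation. Scripting governs what is said to the patient, not who is approached.

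**Working it through.** **Inputs from the documents.** Three arms at 1:1:1; block sizes 3 and 6; one list per coordinator; the coordinator sees all of their own past assignments; 576 patients planned for MOVE IT, 192 per arm (SAP section 7).

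**Assumptions, because the documents are silent.** The mix of block sizes: equal numbers of 3s and 6s as the central case, with all 6s and all 3s as limits. The number of coordinators: two to four. The strength of any selection: 5 percentage points, for illustration only.

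**The plan's own figure.** Simulated lists give 0.333 per arm, matching the stated 33.3%. This is also the chance rate for guessing. The documents give no figure for predictability.

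**Step 1. Best guess in a block of 3.** The chances of being right at positions 1 to 3 are 1/3, 1/2 and 1. The average is (0.3333 + 0.5 + 1)/3 = 11/18 = 61.1%.

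**Step 2. Best guess in a block of 6.** At each position the best guess is the arm with most places left. Averaged over the possible histories, the chances of being right are:

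| Position | Chance correct |
|---|---|
| 1 | 1/3 = 0.3333 |
| 2 | 2/5 = 0.4000 |
| 3 | 1/2 = 0.5000 |
| 4 | (3/5)(2/3) + (2/5)(1/3) = 0.5333 |
| 5 | (1/5)(1) + (4/5)(1/2) = 0.6000 |
| 6 | 1 |

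The sum is 3.3667, and 3.3667/6 = 56.1%.

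**Step 3. Mixed blocks.** With equal numbers of each size, weighted by patients: (3 × 0.6111 + 6 × 0.5611)/9 = 5.2/9 = 57.8%. Simulated lists of 30, 96 and 192 patients give 57.4% to 57.7%. Across all mixes the range is 56.1% to 61.1%.

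**Step 4. What the coordinator must know.** Every completed block leaves the tally level, so the arm used least so far is always the arm with most places left. In simulation, naming that arm did as well as an optimal guesser who knew the two block sizes. A tally is enough.

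**Step 5. Certainty.** If the sizes are known but not their order, about 8% to 9% of assignments are certain (equal mix). If each block's size were known: (3 × 1/3 + 6 × 0.2)/9 = 24.4%.

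**Step 6. Illustrative bias.** Suppose the coordinator approaches a patient 5 points more willing when the tally favours the high offer, and 5 points less willing when it favours the low one. The bias in the high-minus-low enrolment difference on simulated 144-patient lists is:

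| When the coordinator acts | Bias (points) |
|---|---|
| Only when one arm is uniquely least used | 3.0 |
| On every least-used-arm guess | 3.7 |
| Whenever the high and low counts differ | 4.4 |

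Reversing the selection reverses the sign, with the same size.

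**Step 7. Alternatives.**

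| Scheme | Correct guesses |
|---|---|
| Per-coordinator lists, blocks of 3 and 6 | about 58% |
| Per-coordinator lists, blocks of 9, 12 and 15 in equal numbers | (9 × 0.5319 + 12 × 0.5120 + 15 × 0.4973)/36 = 51.1% |
| One hospital-wide blocked list, 2 to 4 coordinators | about 34% to 35% |
| Unrestricted randomisation | 33.3% |

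The hospital-wide row assumes that each coordinator sees only their own assignments and that patients reach the coordinators in random order.

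**The case against.** A reader might infer that concealment fails outright. The documents do not support that. The list is held in the REDCap module, the assignment appears only after eligibility is entered, block sizes vary, and even the best guess is wrong about 42% of the time. The 58% describes a coordinator who tracks every assignment and always guesses. It is what the scheme permits, not a description of anyone's conduct.

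A reader might also infer that coordinators could bend the eligibility screen. Support for this is thin. Final eligibility rests on two factual items, smartphone ownership and participation in other physical activity trials. Only one patient per room is approached, readmitted patients are not approached again, and everyone randomised stays in the analysis. The route that remains is the choice and order of approach from the screening list. The documents neither fix that order nor say that coordinators may choose freely.

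It is also tempting to read the 4.4 points as an estimate of bias. It is not: the 5-point selection is invented, 4.4 comes from the rule that acts most often, and the sign is open. A coordinator keen to fill MOVE IT might keep willing patients for a $0 offer, which would shrink the contrast.

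Finally, stratifying by recruiter has a purpose, because recruiters may differ in how often patients consent. That stands as a cost of the change, and a coordinator covariate meets most of it.

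All these limits stand. None of them removes the predictability, and neither scripting nor intention-to-treat reaches selection before randomisation.

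**Conclusion.** The concern holds as a weakness in concealment, not as shown bias. In MOVE IT the recruiter can predict the next offer about 58% of the time (56% to 61% over every mix of block sizes) against 33% by chance, using nothing more than a tally. The result rests on the stated block sizes, the separate list per coordinator, and a coordinator who keeps count.

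Any effect on the enrolment difference is of unknown size and direction. An assumed 5-point selection gives roughly 3 to 4.4 points either way. No figure is offered for the income or economic well-being interactions. The main cause is the list per recruiter; the short blocks come second.

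**What to change.** **For further randomisation.** In protocol section 7.b and SAP section 3, replace the per-coordinator MOVE IT lists with one hospital-wide REDCap list, either unrestricted or in variable blocks whose sizes are not disclosed to coordinators. Let each coordinator see only their own assignments. Unrestricted randomisation is the safer choice if one coordinator may work alone for long stretches, because that person would then see consecutive entries of a blocked list. Do not rely on larger blocks within coordinator.

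**In the analysis.** Add coordinator as a covariate in the MOVE IT models in SAP section 5.c.

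**For patients already randomised.** The SAP change log is dated January and February 2020 and refers to interim analyses, so much of the sample may already have been allocated under the per-coordinator lists. For these patients, add the coordinator term, rebuild each coordinator's running tally, and check whether baseline covariates track the arm it predicted. The coordinator term alone does not remove selection within a coordinator's own list, so this check is needed as well, and the limitation should be reported.

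**Cost.** A new allocation file, short edits to two sections, one model term and one diagnostic table. Balance within coordinator becomes less exact, which the covariate handles. Overall balance remains adequate: under unrestricted allocation the standard deviation of an arm's size is √(576 × 1/3 × 2/3) = 11.3 around 192.
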